1 SYNOPSIS

Title: A Prospective, Open-Label, Single-Arm, Phase 2, Multicenter Study Evaluating the Efficacy of Venetoclax Plus Ibrutinib in Subjects with T-cell Prolymphocytic Leukemia	
Background and Rationale:	
T-cell prolymphocytic leukemia (T-PLL) is a rare and aggressive T-lymphoid malignancy characterized by proliferation of post-thymic prolymphocytes, usually refractory to current treatment strategies or complicated by relapse and associated with short overall survival.
 
In 2 recent ex vivo drug screening studies, consistent activities of B-cell lymphoma (BCL)-2 inhibition in T-PLL were observed. Venetoclax is a potent, selective, and orally bioavailable small molecule inhibitor of BCL-2 that binds with > 1,000-fold higher affinity for BCL-2 (inhibition rate constant [Ki] < 0.010 nM) than for B cell lymphoma – extra large (BCL-X_L; Ki = 48 nm) or myeloid cell leukemia (MCL)-1 (Ki > 444 nM).
 
As proof of principle, the first-in-human treatment using venetoclax in 2 late-stage subjects with T PLL was reported. Responses were positive; however, potential mechanisms of resistance may develop through BCL-2 and BCL-X_L induction. Therefore, studies testing venetoclax with appropriate combination partners in subjects with T-PLL are warranted. Ex vivo drug combination studies in primary T-PLL subject samples demonstrated that T-PLL cell-specific synergism of venetoclax was highest with ibrutinib. Ibrutinib (IMBRUVICA®) is a first-in-class, potent, orally administered, covalently binding inhibitor of Bruton's tyrosine kinase (BTK) which was co-developed by Pharmacyclics LLC and Janssen Research & Development LLC for the treatment of patients with B-cell malignancies.

Objectives and Endpoints:	
The primary objective is to demonstrate the efficacy in subjects with relapsed or refractory (R/R) T-PLL treated with venetoclax plus ibrutinib.
 
The secondary objectives of this study are:
 
 • To assess safety and tolerability in subjects with T-PLL treated with venetoclax plus ibrutinib. • To assess the ability of the subset of transplant-naïve subjects to proceed to further autologous/allogeneic stem cell transplantation (assessed by number of eligible subjects reaching transplant). • To evaluate the progression-free survival, duration of response, time-to-progression, event-free survival, disease control rate, and overall survival. 
The exploratory objective is to identify biomarker/genetically-defined subgroups regarding response and survival.
 
The primary endpoint is the overall response rate (ORR) in R/R T-PLL subjects.
 
Secondary endpoints include: progression-free survival, duration of response, time-to-progression, event-free survival, disease control rate, overall survival, and number of eligible subjects reaching autologous or allogeneic transplantation.
 
Safety endpoints include evaluation of adverse event (AE) monitoring,

	
physical examinations, vital sign measurements, electrocardiogram variables (if clinically indicated), and clinical laboratory testing (hematology and chemistry) as measures of safety and tolerability for the entire study duration.
 
Plasma samples for venetoclax and ibrutinib will be collected to determine trough concentrations. A nonlinear mixed-effects modeling approach may be used to estimate the population central values and the individual values of venetoclax parameters such as clearance.
 
Biospecimens (blood and bone marrow aspirates and/or biopsy) may be collected at specified time points throughout the study for exploratory analyses of known and/or novel disease-related or drug-related biomarkers. Types of biomarkers may include nucleic acids, proteins, lipids, or metabolites. These biomarker assessments may be used to assess and generate prognostic, predictive, pharmacodynamic, or surrogate biomarker signatures. The analyses may include but are not limited to: molecular profiling of T-PLL cells, ex-vivo sensitivity, and minimal residual disease assessments.

Investigators:	Investigator information is on file at AbbVie.
Study Sites:	Approximately 20 sites in 9 countries: Australia, Austria, Finland, France, Germany, Italy, The Netherlands, United Kingdom, and United States.
Study Population and Number of Subjects to be Enrolled:	
The patient population consists of subjects with R/R T-PLL. The study will enroll 14 subjects with R/R T-PLL in Stage 1 and up to 23 subjects in Stage 2 with a maximal total of 37 subjects (Stage 1 plus Stage 2).
 
Subjects who are treatment-naïve may be enrolled during Stage 2 of the study. The number of treatment-naïve subjects to be enrolled will depend on the required sample size for the R/R subjects in Stage 2 which is based on the number of responders from Stage 1 and considering the maximum of 37 subjects in total to be enrolled in the study.

Investigational Plan:	
This study is an open-label, single-arm, Phase 2, multicenter study evaluating the efficacy of venetoclax plus ibrutinib with an optimal adaptive 2-stage design as follows:
 
 • Stage 1: Enroll 14 subjects with R/R T-PLL and move to Stage 2 if 4 or more responders as follows: 
 • response assessment for Stage 1 will be performed on a continued basis until all 14 subjects have enrolled into Stage 1 and have completed the Week 24 disease assessment • Stage 2: Enroll up to an additional 23 subjects 
Safety will be continuously assessed and dose adjustments will be considered for both venetoclax and ibrutinib.
 
Interim analysis will occur after Stage 1. The study will stop for futility if the number of responders at Stage 1 is ≤ 3. If 4 or more subjects respond prior to enrolling all 14 subjects in Stage 1, enrollment will not pause between stages. The maximal sample size will be 37 subjects. If there are 7 or more responders out of 14 subjects in Stage 1, 17 subjects with R/R T-PLL will be enrolled in Stage 2.

Key Eligibility Criteria:	Male or female subjects, at least 18 years old, with a diagnosis of T-PLL that

	
requires treatment and suitable for oral administration of study drugs. Subjects should meet the following disease activity criteria: an Eastern Cooperative Oncology Group performance status ≤ 2.
 
Subjects should have laboratory values meeting the following criteria:
 
 alanine aminotransferase/aspartate aminotransferase $\leq 3 \times$ the upper limit of normal (ULN); adequate liver function as indicated by a total bilirubin $\leq 1.5 \times$ ULN (subjects with documented Gilbert's syndrome may have bilirubin $> 1.5 \times$ ULN); absolute neutrophil count $> 1000/\mu\text{L}$; platelet count $> 50,000/\mu\text{L}$; creatinine clearance ≥ 50 mL/minute; and hemoglobin > 8 g/dL.

Study Drug and Duration of Treatment:
	
Ibrutinib 420 mg will be dosed orally (PO), once daily (QD) starting on Day -1.
 
Venetoclax will be initiated on Week 1, Day 1 with an initial 5-day dose ramp-up for venetoclax. Venetoclax 400 mg (target dose) will be dosed PO, QD; an option to increase the dose of venetoclax to 600 mg QD will be available at Week 8 or thereafter if there is evidence of incomplete response and/or if the dose of ibrutinib has been decreased to 280 mg/day or 140 mg/day due to toxicity management. The dose of venetoclax should not be increased to 600 mg/day in subjects with significant venetoclax toxicity. The maximum dose allowed for venetoclax is 600 mg/day.
 
Treatment duration of combination treatment will be as follows:
 
 eligible subjects will proceed to stem cell transplantation after reaching complete remission (CR) (combination therapy will be discontinued but subjects will be followed for disease progression) 2 years, will be given to subjects who are ineligible for stem cell transplantation unless treatment is intolerable or the subject develops progressive disease 
For subjects who continue to derive clinical benefit after 2 years of treatment, AbbVie will work with the investigator to consider the potential continuation of therapy, as per local regulations.

Date of Protocol Synopsis:
	
11 November 2020

2 INTRODUCTION

2.1 Background and Rationale

Why Is This Study Being Conducted

T-cell prolymphocytic leukemia (T-PLL) is a rare and aggressive T-lymphoid malignancy characterized by proliferation of post-thymic prolymphocytes, usually refractory to current treatment strategies or complicated by relapse and associated with short overall survival. Patients with T-PLL typically experience elevated and exponentially rising lymphocyte counts along with splenomegaly, hepatomegaly, lymphadenopathy, and effusions. Responses to alkylating agents, purine analogs, and polychemotherapy are poor, ranging from 20% to 53% in mostly previously untreated patients with short survival durations. There is very scarce clinical data for the overall response rate (ORR) in the relapsed or refractory (R/R) patient population and the ORR is not expected to be greater than 20%. Therefore, in pretreated patients, responses to non-alemtuzumab therapy are estimated to achieve an ORR of 20%.^{1,2,3}

The use of the monoclonal anti-CD52 antibody alemtuzumab has improved response rates of 50% to 75% or even higher (up to 90%) when applied in the first-line setting.^{4,5} Based on data available, benefit (if any) from a combination of alemtuzumab with purine analogs or polychemotherapy compared to alemtuzumab alone is unclear. Thus far, alemtuzumab remains the most effective treatment option in patients with T-PLL; however, despite relatively high response rates (50% to 90%), all patients eventually relapse with a median progression-free survival (PFS) of less than 12 months. Allogeneic stem cell transplantation is considered a treatment goal for eligible patients since long survival durations have been observed.

In 2 recent ex vivo drug screening studies, consistent activities of B-cell lymphoma (BCL)-2 inhibition in T-PLL were observed.^{6,7} Venetoclax is a potent, selective, and orally bioavailable small molecule inhibitor of BCL-2 that binds with > 1,000-fold higher affinity for BCL-2 (inhibition rate constant [Ki] < 0.010 nM) than for B-cell lymphoma – extra large (BCL-X_L; Ki = 48 nM) or myeloid cell leukemia (MCL)-1 (Ki > 444 nM). Venetoclax (also referred to as ABT-199, A-1195425.0, GDC-0199, RO5537382, Venclexta[®], and Venclyxto[®]) is currently being evaluated for the treatment of patients with chronic lymphocytic leukemia (CLL), small lymphocytic lymphoma (SLL), acute myeloid leukemia (AML), multiple myeloma, and non-Hodgkin's lymphoma (NHL).

Venetoclax is currently approved in the United States (US) for the treatment of patients with CLL or SLL with or without 17p deletion and who have received at least 1 prior therapy. In addition, venetoclax was granted a conditional marketing authorization from the European commission for the following indication: Venclyxto monotherapy is indicated for the treatment of CLL in the presence of 17p deletion or tumor protein p53 (TP53) mutation in adult patients who are unsuitable for or have failed a B-cell receptor inhibitor (BCRi) or in the absence of 17p deletion or TP53 mutation in adult patients who have failed both chemoimmunotherapy and a BCRi. As of July 2018, marketing authorizations have been granted in the US, European Union, Canada, and more than 20 additional countries worldwide.

As proof of principle, the first-in-human treatment using venetoclax in 2 late-stage subjects with T-PLL was reported.⁷ Responses were positive; however, potential mechanisms of resistance may develop

through BCL-2 and BCL-X_L induction. Therefore, studies testing venetoclax with appropriate combination partners in subjects with T-PLL are warranted. Ex vivo drug combination studies in primary T-PLL subject samples demonstrated that T-PLL cell-specific synergism of venetoclax was highest with ibrutinib.⁸ Ibrutinib (IMBRUVICA[®]) is a first-in-class, potent, orally administered, covalently binding inhibitor of Bruton's tyrosine kinase (BTK) which was co-developed by Pharmacyclics LLC and Janssen Research & Development LLC for the treatment of patients with B-cell malignancies. Ibrutinib has been approved in many regions globally including the US and European Union for adult patients in one or more of the following indications: CLL/SLL including CLL/SLL with a 17p deletion; mantle cell lymphoma in patients who have received at least 1 prior therapy; Waldenström's macroglobulinemia; marginal zone lymphoma who require systemic therapy and who have received at least 1 prior anti-CD20-based therapy; and chronic graft versus host disease following the failure of 1 or more lines of systemic therapy. For further details, please refer to the IMBRUVICA[®] (ibrutinib) Investigator's Brochure.⁹

Preliminary clinical response from 1 subject treated with venetoclax in combination with ibrutinib was recently reported at the 23rd Congress of the European Hematology Association;⁸ clinical response was demonstrated by significant clinical improvement, significant decrease in spleen size, and improvement in disease-related laboratory values such as leukocytosis, lactate dehydrogenase, and β 2 microglobulin (B2M).

Clinical Hypothesis

The combination of venetoclax with ibrutinib can be safely administered and will result in a greater percentage of subjects who achieve a best ORR (complete remission [CR]/CR with incomplete bone marrow recovery [CRi] + partial response [PR]).

In subjects with R/R T-PLL, the treatment with venetoclax plus ibrutinib will be considered promising if the combination yields a best ORR of 40% or greater. A poor rate is defined a best ORR of 20% or less based on the previously available data.

2.2 Benefits and Risks to Subjects

Effective treatment options remain dismal for patients with R/R T-PLL as well as for treatment-naïve patients who have no access or are ineligible to treatment with alemtuzumab. While clinical trials are the recommended treatment option for both treatment-naïve and R/R patients by treatment guidelines (e.g., National Comprehensive Cancer Network [NCCN] guidelines), as of August 2018 there are currently no ongoing interventional clinical studies specific to this rare disease.

The recently reported ex vivo data and very limited subject data provide rationale for a clinical study with the combination of venetoclax and ibrutinib. Clinical data from this same combination target dose regimen has also recently been presented for a different indication (i.e., CLL [CAPTIVATE study]). Early data from 163 subjects show a spectrum of adverse events (AEs) consistent with the historic safety profile of single-agent ibrutinib and single-agent venetoclax with no new safety signals and promising activity (77% undetectable minimal residual disease [MRD] in peripheral blood after 6 months of therapy).⁸

For further details, please see findings from completed studies including safety data in the venetoclax Investigator's Brochure¹⁰ and the ibrutinib Investigator's Brochure.⁹

Considering the coronavirus disease – 2019 (COVID-19) pandemic, the benefit and risk to subjects participating in this study has been re-evaluated. Based on the limited information to date, no additional risk to study participants is anticipated with the use of venetoclax plus ibrutinib.

3 STUDY OBJECTIVES AND ENDPOINTS

3.1 Objectives

Primary

- To demonstrate the efficacy in subjects with R/R T-PLL treated with venetoclax plus ibrutinib.

Secondary

- To assess safety and tolerability in subjects with T-PLL treated with venetoclax plus ibrutinib.
- To assess the ability of the subset of transplant-naïve subjects to proceed to further autologous/allogeneic stem cell transplantation (assessed by number of eligible subjects reaching transplant).
- To evaluate the PFS, duration of response, time-to-progression, event-free survival, disease control rate, and overall survival.

Exploratory

- To identify biomarker/genetically-defined subgroups regarding response and survival.

3.2 Primary Endpoint

The primary endpoint is the ORR which is defined as the proportion of subjects achieving CR, CRi, or PR as their best overall response (per investigator assessment) in R/R T-PLL subjects based on the T-PLL consensus criteria 2019 (refer to the Operations Manual Section 3.14).^{1,11}

3.3 Secondary Endpoints

Key secondary endpoints are as follows:

- PFS, defined as the time from the date of first dose of any study drug to the date of earliest disease progression or death
- duration of response, defined for subjects who achieve a best overall response of CR, CRi, or PR, as the time from the date of first response (CR, CRi, or PR) to the earliest date of disease progression or death
- time-to-progression, defined as the time from the date of first dose of any study drug to the date of earliest disease progression

- event-free survival, defined as the time from the date of first dose of any study drug to the date of earliest disease progression, death, or start of a new anti-T-PLL therapy
- disease control rate, defined as the proportion of subjects achieving CR, CRi, PR, or stable disease as best overall response
- overall survival, defined as the time from the date of first dose of any study drug to death from any cause
- number of eligible subjects reaching autologous or allogeneic transplantation; eligible subjects are the transplant-naïve subjects who have achieved CR

All secondary endpoints will be assessed per investigator assessment in R/R T-PLL subjects based on the T-PLL consensus criteria 2019.¹¹

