Ibrutinib 420 mg will be dosed orally (PO), once daily (QD) starting on Day –1. Venetoclax will be initiated on Week 1, Day 1 with an initial 5-day dose ramp-up for venetoclax ([Figure 1](#)). Venetoclax 400 mg (target dose) will be dosed PO, QD; an option to increase the dose of venetoclax to 600 mg QD will be available at Week 8 or thereafter if there is evidence of incomplete response and/or if the dose of ibrutinib has been decreased to 280 mg/day or 140 mg/day due to toxicity management. The dose of venetoclax should not be increased to 600 mg/day in subjects with significant venetoclax toxicity. The maximum dose allowed for venetoclax is 600 mg/day.

Treatment duration of combination treatment will be as follows:

- eligible subjects will proceed to stem cell transplantation after reaching CR (combination therapy will be discontinued but subjects will be followed for disease progression)
- up to 2 years, will be given to subjects who are ineligible for stem cell transplantation unless treatment is intolerable or the subject develops progressive disease

[figure not shown]
For subjects who continue to derive clinical benefit after 2 years of treatment, AbbVie will work with the investigator to consider the potential continuation of therapy, as per local regulations.

See Section 5 for information regarding eligibility criteria.

The dosing schematic is shown in Figure 1. To mitigate the risk of tumor lysis syndrome (TLS) (see Section 6.2) with venetoclax, a 5-step dose ramp-up with hospitalization for close monitoring and prophylaxis has been developed. Due to the aggressive nature of T-PLL, the venetoclax ramp-up will be administered in a daily manner, starting with 20 mg on Week 1, Day 1 and reaching the target dose of 400 mg on Week 1, Day 5. Refer to Section 6.2 for details for TLS management.

Further information regarding study procedures is located in the Operations Manual Section 3.

Figure 1. Dosing Schematic

CR = complete remission; D = day; W = week

Note: Venetoclax 5-step dose ramp-up in 5 days to target dose of 400 mg daily with an option to increase the dose to 600 mg QD at Week 8 or thereafter if there is evidence of incomplete response and/or if the dose of ibrutinib has been decreased to 280 mg/day or 140 mg/day due to toxicity management.

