3.11 Post-Treatment Follow-Up and Survival Visits

Subjects who discontinue study drug but have not experienced progressive disease (PD) will return for post-treatment follow-up visits. The post-treatment follow-up visits will follow the same schedule as the visit schedule (i.e., Week 4, Week 8, Week 12, Week 16, Week 24, Week 36, and every 12 weeks thereafter). Subjects will return for post-treatment follow-up visits until study completion starting from study drug discontinuation until documented PD or other post-treatment therapies (including stem cell transplantation) are received. Follow-up hematology and disease response assessment data will be collected.

Survival information (i.e., the date and cause of death) will be collected via telephone calls at 6-month intervals or as needed to allow for more frequent survival analyses.

All subjects will be followed for survival information (i.e., date and cause of death, all poststudy anticancer treatment including stem cell transplantation, reasons for poststudy anticancer treatment, regimens, dates of initiation and completion, etc.) unless the subject requests to be withdrawn from the

study survival follow-up; this request must be documented in the subject's medical record and signed by the investigator. If the subject withdraws from study follow-up, the study staff may use a public information source (such as county records) to obtain information about survival status only, as appropriate per local regulations.

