Complete Remission (CR): all of the response criteria have to be met.

Complete Remission with Incomplete Marrow Recovery (CRi): all of the CR response criteria in Group A have to be met and at least 1 parameter in Group B is not achieved.

Partial Remission (PR): at least 2 of the parameters in Group A and 1 parameter in Group B need to improve if previously abnormal. If only one parameter of both Groups A and B is abnormal prior to therapy, only 1 parameter needs to improve.

Stable Disease (SD): all of the above criteria have to be met. This state needs to be sustained for at least 3 months.

Progressive Disease (PD): at least one of the above criteria of Group A or Group B has to be met. Constitutional symptoms alone do not define PD.

Table 3. Confirmatory Response Criteria (Based on CT and Bone Marrow Assessments)

Group	Parameter	Complete Remission (all met)	Partial Remission (≥ 2 in Group A and ≥ 1 in B met)	Stable Disease (all met)	Progressive Disease (≥ 1 in Group A or B met)
A	Lymph nodes by CT/MRI	All long-axis diameters to < 1.0 cm	Decrease ≥ 30% in SLD	Change of -29% to +20% in SLD	Increase in > 20% in SLD from Nadir ^a
	Spleen by CT/MRI	Spleen < 13 cm	Decrease ≥ 50% in vertical length beyond normal from baseline	Change of -49% to +49% beyond normal from baseline	Increase ≥ 50% in vertical length beyond normal from baseline
	Constitutional symptoms	None	Any	Any	Any
	Circulating lymphocyte count	< 4 × 10 ⁹ /L	≤ 30 × 10 ⁹ /L and decrease ≥ 50% from baseline	> 30 × 10 ⁹ /L or change of -49% to +49%	Increase ≥ 50% from baseline ^b
	Bone marrow only to assess if CT/MRI confirms CR/CRi	T-PLL cells < 5% of mononuclear cells	Any	Any	Any
	Any other specific site involvement ^c by CT/MRI	None	Any	Any	Any

Group	Parameter	Complete Remission (all met)	Partial Remission (≥ 2 in Group A and ≥ 1 in B met)	Stable Disease (all met)	Progressive Disease (≥ 1 in Group A or B met)
B	Platelet count	≥ 100 × 10 ⁹ /L (untransfused)	≥ 100 × 10 ⁹ /L or increase ≥ 50% from baseline	Change of -49% to +49%	Decrease of ≥ 50% from baseline
	Hemoglobin	≥ 11.0 g/dL (untransfused, independent of erythropoietin)	≥ 11 g/dL or increase ≥ 50% from baseline	< 11.0 g/dL or increase < 50% from baseline or decrease < 2 g/dL	Decrease of ≥ 2 g/dL from baseline
	Neutrophils	≥ 1.5 × 10 ⁹ /L (independent of growth factor)	≥ 1.5 × 10 ⁹ /L or increase ≥ 50% from baseline	Change of -49% to +49%	Decrease of ≥ 50% from baseline

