4.3.2 Secondary Efficacy Endpoints

The following are the secondary efficacy endpoints in the study: PFS, DoR, TTP, EFS, OS, total number of eligible subjects (transplant-naïve subjects who have achieved CR) reaching autologous or allogeneic transplantation.

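### The transplant endpoint leaves transplants reached in CRi or PR untabulated, and the SAP 6.4 proportion, read literally, is always 100%

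*Protocol*

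**What the plan says.** The secondary objective in Protocol 3.1 is "To assess the ability of the subset of transplant-naïve subjects to proceed to further autologous/allogeneic stem cell transplantation (assessed by number of eligible subjects reaching", the sentence ending with the word transplant. The endpoint in Protocol 3.3 then says who is eligible: "eligible subjects are the transplant-naïve subjects who have achieved CR". SAP 4.3.2 lists the same endpoint, also as a count: "total number of eligible subjects (transplant-naïve subjects who have achieved CR) reaching autologous or allogeneic transplantation".

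The planned pathway in Protocol 4.1 is that "eligible subjects will proceed to stem cell transplantation after reaching CR". SAP 6.3 follows it: for PFS and TTP, a transplant escapes being treated as non-protocol therapy only in an eligible subject with CR.

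Elsewhere CR does not include CRi or PR. The primary endpoint is "the proportion of subjects achieving CR, CRi, or PR as their best overall response", which names the three side by side. The Operations Manual (Protocol Appendix I), section 3.14, defines CRi thus: "all of the CR response criteria in Group A have to be met and at least 1 parameter in Group B is not achieved". Group A includes the marrow; Group B is platelets, hemoglobin and neutrophils.

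Survival follow-up in Operations Manual 3.11 collects "all poststudy anticancer treatment including stem cell transplantation" for all subjects, whatever their response.

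SAP 6.4 describes the transplant measure again. There it is a proportion, and eligible subjects must be transplant-naïve, have reached CR, and have gone on to transplant.

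**The concern.** The clinical question behind the objective is how many transplant-naïve subjects the regimen brings to transplant. The planned count answers a narrower question, because it starts from subjects who reached CR on treatment. A subject in CRi has cleared every disease criterion that a CR subject has and differs only in a blood count, which Operations Manual 3.14 attributes to drug toxicity rather than T-PLL. That subject is a responder for ORR, yet a transplant in CRi is not counted. The same holds for a transplant in PR.

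CRi is plausible here. Protocol 5.1 admits subjects with neutrophils just above 1000/µL, platelets just above 50,000/µL and hemoglobin just above 8 g/dL. CR requires at least 1.5 × 10⁹/L, 100 × 10⁹/L and 11 g/dL. A subject can therefore enter below all three Group B thresholds.

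What is at stake is how a secondary, descriptive result is read. A report could show few transplants although more subjects reached one, or could show a proportion of 100% that carries no information.

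**Working it through.** The documents state no transplant figure to reproduce. The check sets the definitions side by side and then gives an illustration under stated assumptions.

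**1. The count (Protocol 3.3, SAP 4.3.2).** Among transplant-naïve R/R subjects, let T_CR be the transplants in subjects who reached CR, and T_other those in subjects who did not (CRi, PR or other).

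- Reported count = T_CR.
- All transplants = T_CR + T_other.
- Share not counted = T_other / (T_CR + T_other).

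The reported count can equal the total or fall below it, never exceed it. If T_other = 0 the share is 0%.

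**2. The proportion (SAP 6.4).** The numerator is transplant-naïve subjects with CR who were transplanted. The denominator is eligible subjects, and 6.4 makes transplantation part of eligibility. So the proportion is T_CR / T_CR = 100% if T_CR ≥ 1, and undefined if T_CR = 0. Under the Protocol 3.3 definition, the denominator would be all transplant-naïve subjects with CR.

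**3. Illustration.** From the documents: at most 37 R/R subjects, and an ORR of 40% under the alternative, giving 37 × 0.40 = 14.8 responders. Assumed, because the documents are silent: all subjects are transplant-naïve, 50% of CR subjects are transplanted, CR makes up 50% or 25% of responders, and 0% to 50% of CRi/PR responders are transplanted.

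- CR share 50%: counted = 14.8 × 0.50 × 0.50 = 3.7; CRi/PR responders = 14.8 × 0.50 = 7.4.
- CR share 25%: counted = 14.8 × 0.25 × 0.50 = 1.85; CRi/PR responders = 14.8 × 0.75 = 11.1.

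| CR share of responders | CRi/PR responders transplanted | Counted | Not counted | Share not counted | Counted / 37 | All transplants / 37 |
|---|---|---|---|---|---|---|
| 50% | 0% | 3.7 | 0 | 0% | 10% | 10% |
| 50% | 10% | 3.7 | 0.74 | 17% | 10% | 12% |
| 50% | 25% | 3.7 | 1.85 | 33% | 10% | 15% |
| 50% | 50% | 3.7 | 3.7 | 50% | 10% | 20% |
| 25% | 0% | 1.85 | 0 | 0% | 5% | 5% |
| 25% | 10% | 1.85 | 1.11 | 38% | 5% | 8% |
| 25% | 25% | 1.85 | 2.78 | 60% | 5% | 12.5% |
| 25% | 50% | 1.85 | 5.55 | 75% | 5% | 20% |

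In every row, half of the CR subjects are transplanted by assumption (for example 3.7 / 7.4 = 50%). SAP 6.4 read literally would report 3.7 / 3.7 = 100%.

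**The case against.** The strongest reply is that the restriction is deliberate and consistent. The objective says in its own parenthesis that it is measured by eligible subjects, Protocol 3.3 defines them, Protocol 4.1 plans transplant after CR, and the SAP treats only that transplant as part of the protocol. Against that target the count is complete. This stands: a reader who takes the objective without its parenthesis might infer that objective and endpoint contradict each other, and they do not.

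A reader might also infer that the trial will undercount transplants, or that CRi will be the commoner form of complete remission. The documents support neither. They give no frequency of CR, CRi or transplant. The gap between entry thresholds and CR thresholds makes CRi possible but supplies no rate. A subject who moves from CRi to CR before transplant would also be counted.

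The endpoint is secondary and untested, in a study that SAP 4.6 describes as hypothesis generating. Transplants are recorded whatever the response, so a wider table could be made at reporting. That is true, but choosing the count after seeing the results is weaker than naming it beforehand.

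None of this answers the SAP 6.4 point. The counts in Protocol 3.3 and SAP 4.3.2 have no denominator and are not circular; the proportion in 6.4 is.

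**Conclusion.** The point holds in a limited form. The CR-only count is a legitimate measure of the planned pathway, but neither document plans to report how many transplant-naïve subjects reach transplant by any route. The size of the gap is unknown before data: zero if no transplant takes place outside CR, and 17% to 75% of transplants in the other illustrated scenarios. Those percentages follow from the assumed inputs and are not predictions.

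The SAP 6.4 definition is a wording defect that needs no assumption. It also differs in kind from a low count: it forces the proportion to its maximum. Primary endpoint, sample size and error rates are unaffected. The programming plan to which the SAP refers is not among the documents, so a table specified only there could not be seen.

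**What to change.** Change the analysis text only; no clinical rule is touched.

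- Keep the CR-based count of Protocol 3.3 and SAP 4.3.2 as one row.
- Add the number and proportion of all transplant-naïve FAS subjects who reach transplant, split by last response before transplant: CR, CRi, PR, other.
- In SAP 6.4, drop transplantation from the definition of eligible. Use transplant-naïve subjects with CR as the denominator of the CR row, and all transplant-naïve FAS subjects as the denominator of the broader row.
- State that the CR row depends on ever having reached CR while the split uses the last response, so the two may differ for a subject whose response changed.

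The cost is a few lines of SAP text and one descriptive table. Prior treatment comes from the oncology history (Operations Manual 3.2), response from the scheduled assessments, and later transplants from survival follow-up (Operations Manual 3.11). The small downside is that the broader row includes transplants outside the protocol's CR pathway, which is why it should always be shown by response.
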